The HCW FGD will use the Consolidated Framework for Implementation Research (CFIR) to elicit information about health worker experiences with specific implementation strategies and opinions on modifications to these strategies to further improve implementation outcomes of fidelity and penetration.

PrEP Policy Maker and Implementer IDI: We will use qualitative methods to explore knowledge, attitudes, and beliefs about PrEP delivery strategies, preferred and essential attributes for PrEP delivery best practices, and experiences with PrEP delivery at national, county, or partner organization level.

12.2.6) LABORATORY METHODS

Not applicable

12.2.7) DATA COLLECTION INSTRUMENTS

- PrEP user focus group guide
- PrEP user demographic information
- HCW Survey
- HCW FGD guide
- Service Availability and Readiness Assessment Tool
- PrEP policy maker and implementer interview guide

12.2.8) VARIABLES: Outcomes, indicators, and source documents

Not applicable

12.2.9) TRAINING PROCEDURES

Drs. [name] and [name] will supervise training of facilitators for the qualitative components of the study.

Study Materials

- HCW FGD Consent Form
- HCW Survey Consent Form
- Policy Maker IDI Consent Form
- PrEP User FGD Consent Form

12.3 AIM 2:

To pilot and evaluate four strategies or bundles of strategies for optimized PrEP delivery for impact on penetration, fidelity, timeliness, efficiency, client and HCW satisfaction (including time), client PrEP knowledge, PrEP continuation, and PrEP adherence. We will test three strategies identified by stakeholders (based on qualitative information from Aim 1) and 1 pre-developed package of strategies (video counseling, HIVST, and optimized delivery). Operational definitions of each outcome are provided in Section *11.3.9 Variables*.

	Aim 2					
	Implementation strategy tests					
Population	HCW, clients attending study clinics					
Design	Interrupted time series (ITS) quasi-experimental design					
Data collection	Register abstraction of existing program data, client observation, quantitative surveys					
	Register abstraction of existing program data: unable to predict total number of records to be abstracted; expected abstraction of ~200 clients per month per clinic					
Sample size	Client observations: up to 200 clients per clinic per interrupted time series experiment cycle					

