	Quantitative surveys: up to 240 clients per clinic per interrupted time series experiment cycle; up to 20 HCW per clinic per interrupted time series experiment cycle					
Outcome(s) of interest	PrEP penetration, fidelity, uptake, continuation, adherence, efficiency, timeliness, client and HCW satisfaction, client PrEP knowledge, service availability					
	HCW: work at a facility involved in study, involved in PrEP service delivery, >18 years					
criteria	Clients: female clients seeking health services at study facilities, >15 years (includes emancipated minors)					
Exclusion criteria	n N/A					

12.3.1) STUDY DESIGN

We will utilize interrupted-time series design; this is a quasi-experimental design that compares data before an intervention is introduced to data after the intervention is introduced, and controls for time trends (Figure 8). Four rounds of interrupted-time series evaluations to evaluate four PrEP optimization interventions, three identified by

stakeholders based on qualitative information in Aim 1, and one pre-developed package of interventions (video-based PrEP counselling, HIV Self-Testing [HIVST], and optimized PrEP delivery). Each of the four rounds of interrupted-time series evaluations will include 4 facilities receiving the intervention and 4 facilities serving as an ongoing concurrent comparator group; these 4 facilities will not receive any of the packages of interventions, but will undergo the same data collection procedures. There will be three months of baseline data collection and a three month intervention period for each of the 4 intervention facilities, and six months of data collection during the same calendar period for each of the 4 comparator clinics for each of the 4 interrupted-time series interventions.

Figure 8: Interrupted time series experiment design and timeline

12.3.2) INTERVENTION DETAILS

There will be four strategies or bundles of strategies tested, one bundle in each of the four interrupted-time series evaluations. Three of the bundles of strategies will be determined based on the qualitative information gathered

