in Aim 1 by stakeholders and are unknown at this time. One bundle of strategies pre-developed is and includes 3 components: video-based PrEP counselling, HIV Self-Testing [HIVST] for women undergoing repeat HIV testing, and optimized PrEP delivery and prescription processes (Figure 9). We will work with a videography company to develop the PrEP video-based counseling component. We will borrow processes from ongoing and recently completed

Figure 9: Pre-determined bundle of implementation strategies

studies in western Kenya related for optimizing PrEP dispensing and HIVST while clients wait. PrEP will be stored in MCH clinics. Once women ask for PrEP and have been confirmed eligible, women will receive PrEP at MCH clinic. In our prior work, we have arranged with pharmacy and CCC to maintain supplies of PrEP at MCH. HIVST will be provided as an option in private cubicle-style kiosks, which have been tested in western Kenya and found to be acceptable and feasible.

12.3.3) STUDY POPULATIONS

The twenty (20) health care facilities that were included in Aim 1 surveys will be included in the implementation and evaluation of PrEP optimization strategies identified through Aim 1 activities. Of the 20 facilities, facilities will be assigned one of four intervention groups (4 facilities per group) or a comparator group (4 facilities) throughout the four interrupted-time series rounds. Up to twenty HCW will be approached at each facility per interrupted time series cycle to participate in a satisfaction survey to understand their experience with the PrEP optimization intervention.

During each of the four interrupted-time series rounds, we will abstract all clinical records for HIV-negative patients receiving MCH services to assess penetration of PrEP screening and PrEP uptake. We anticipate abstracting records for up to 200 clients per month per clinic (1,200 abstracted records per facility per interrupted-time series). Additionally, to assess intervention fidelity and client satisfaction through exit surveys with up to 40 clients per month per facility (240 exit surveys per facility per ITS). We will assess client time using client observation with up to 200 clients per clinic per interrupted-time series cycle.

12.3.4) SAMPLE SIZE DETERMINATION AND FORMULAS USED

To maintain the greatest amount of power, outcome estimates will be based on individual count data, not aggregated to summaries. We utilized Stata 14 for sample size calculations.

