- Time period: Each experiment will include 3 months of data before each strategy is introduced and 3 months after each strategy is introduced
- Sample size (facilities): There will be 4 experiments, each will include 4 intervention facilities (16 facilities) and the same 4 comparator facilities; for a total of 20 facilities.
- Sample size (participants): We will observe 200 clients per clinic per experiment. We will collect survey data from 240 clients and 20 HCW per clinic per experiment. We will abstract register data during each experiment; while we are unable to predict total number of records to be abstracted, we expect abstraction of ~200 clients per month per clinic.
- Assumptions: α=0.05, two-sided tests, a conservative harmonic mean of 100 women presenting to ANC per month (~600 women over 6 months) per cluster (mean in PrIYA sites was ~163 per month), and a conservative estimate of the coefficient of variation of 0.5. We assume that penetration of PrEP screening and counselling is 68% (SD: 18%), time spent by HCW on PrEP services is 18 minutes (SD: 8 minutes) per PrEP initiator and 13 minutes (SD: 6 minutes) per PrEP-non-initiator, uptake is 10.5% (SD: 5%), and that knowledge and satisfaction scores are on a 100-point scale and have an SD of 20.

- Detectable effect size: We will be able to detect an absolute change of +/-4.8% for outcomes of penetration of PrEP screening, an absolute change of +/- 2 minutes in time, an absolute change of +/1% in PrEP uptake, and an absolute difference of 4 points in knowledge and satisfaction scores.
- Power: We will have at least 80% power

12.3.5) RECRUITMENT PROCEDURES

Register abstraction: We will not actively recruit individual participants for register abstraction.

Client observation: Women receiving MCH services will be approached as they enter the facility and asked to carry a time card. Each time card will collect the time that each service starts and ends and will be filled by providers, but will not collect any identifying information. Study staff will be posted at each facility until the sample size is reached.

Surveys with clients: Women receiving MCH services will be approached as they exit the facility and asked to participate in a brief survey. Study staff will be posted at each facility until the sample size is reached.

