12.3.6 ENROLLMENT & STUDY PROCEDURES

Register abstraction

Consent: Individual patients will not be asked to provide consent as abstracted data are anonymous and it would not be feasible to contact clients to seek consent.

Procedures: We will abstract anonymous patient level count data from health registers at all of the intervention and comparator facilities. We will abstract the following count data from registers: women screened for PrEP interest (penetration), women offered HIV testing and PrEP (fidelity), women who initiate PrEP (uptake), women who adhere to PrEP (adherence determined via pill count), and women who refill PrEP (continuation).

Client observation

Consent: Individual patients will be given the opportunity to verbally accept or decline to carry cards; data are anonymous.

Procedures: A trained research assistant will conduct flow mapping (physical walk throughs to graphically represent patient flow pathways in a facility) and conduct time-and-motion data collection (counting minutes spent waiting and receiving various services) to describe the flow of women within health facilities and between providers as they receive services. Individual patients will be given the opportunity to carry a single sheet of paper with a study identification number to each service delivery point. Health care workers or research assistants will note the time that services begin and end. We will characterize the following outcomes: efficiency and time spent by HCW and clients.

Surveys with clients

Consent: Women will be given the opportunity to provide oral informed consent for participation or to decline participation; these surveys are anonymous.

Procedures: Women will complete a survey following service delivery completion. The following data will be collected via survey: client satisfaction with services, client PrEP knowledge, client perception of being offered PrEP services.

SARA Surveys with HCW

Consent: HCW will be given the opportunity to provide oral informed consent for participation or to decline participation; these surveys are anonymous.

Procedures: HCW will complete a survey. The following data will be collected via survey: HCW satisfaction with training and service delivery modifications.

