Planned Analyses: We will use interrupted time series methodology to compare changes in penetration (PrEP screening), uptake (PrEP initiation), adherence, and continuation (PrEP refills) between the baseline and intervention periods for intervention facilities and with the comparison facilities.

12.3.7) LABORATORY METHODS

Not applicable

12.3.8) DATA COLLECTION INSTRUMENTS

- Exit Survey
- Record abstraction form

12.3.9) VARIABLES: Outcomes, indicators, and source documents

Outcome	Indicator	Source documents
PrEP penetration	Proportion of women who are screened for PrEP / total women receiving antenatal or postnatal services	Routine program data; PrEP register, antenatal register, postnatal register, family planning register
PrEP fidelity	Proportion of women who receive all PrEP specific steps in a visit: HIV testing, HIV risk screening, PrEP counseling	Primary data of anonymous exit survey assessing services received Direct observation of client-provider interactions
		Routine program data: HIV testing register, PrEP register, antenatal register, postnatal register, family planning register
PrEP uptake	Proportion of women who accept PrEP among those offered	Routine program data: PrEP register
PrEP continuation	Proportion of women who present for a refill among those initially prescribed PrEP	Routine program data: PrEP register, pharmacy records
PrEP adherence	Proportion of women who have >80% adherence to PrEP by pill count among those initially prescribed PrEP	Routine program data: PrEP register, pharmacy records
PrEP efficiency	Patient flow mapping to identify more efficient client flows with fewer transitions between physical spaces and providers	Primary data collection through direct observation of patient flow
Timeliness	Time and motion data to assess wait times, service delivery times, and HCW burden	Primary data collection through direct observation and time collection
Client satisfaction	Satisfaction on a scale of 1-10 adapted from Training Satisfaction Survey	Primary data collection through anonymous surveys
HCW satisfaction	Satisfaction on a scale of 1-10 adapted from Training Satisfaction Survey	Primary data collection through anonymous surveys
Client PrEP knowledge	10 questions based on content covered in counseling sessions	Primary data collection through anonymous surveys

12.3.10) TRAINING PROCEDURES

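### Aim 2 promises an effect on health care worker satisfaction, but the survey as described asks only about training and changes that staff at baseline and in comparator clinics have not experienced

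*Combined protocol and SAP*

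**What the plan says.** Section 12.3 sets out to evaluate the four strategies for impact on a list of outcomes that includes "client and HCW satisfaction (including time), client PrEP knowledge, PrEP continuation, and PrEP adherence". HCW satisfaction also has its own row in the outcome table of Section 12.3.9, with the indicator "Satisfaction on a scale of 1-10 adapted from" a training satisfaction questionnaire.

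The design in Section 12.3.1 supplies two possible counterfactuals. One is time: "There will be three months of baseline data collection and a three month intervention period for each of the 4 intervention facilities". The other is the comparator group, of which the plan says "these 4 facilities will not receive any of the packages of interventions, but will undergo the same data collection procedures".

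For the HCW survey itself, Section 12.3.6 names one content area: "HCW satisfaction with training and service delivery modifications". Section 12.3.3 gives a matching purpose: up to twenty HCW per facility and cycle are approached "to participate in a satisfaction survey to understand their experience with the PrEP optimization intervention". Section 12.3.4 states, at 80% power or more, that the study can detect "an absolute difference of 4 points in knowledge and satisfaction scores", without saying whose satisfaction is meant. The planned-analysis paragraph of Section 12.3.6 applies the interrupted time series comparison to penetration, uptake, adherence and continuation; HCW satisfaction is not on that list.

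**The concern.** An effect needs the same quantity measured with and without the strategy. A rating of a modification can be given only by someone who has worked with it. During the three baseline months no strategy is in place, and comparator clinics never receive one. If the questionnaire holds only what Section 12.3.6 describes, the ratings that can be interpreted come from intervention clinics after introduction. They show whether staff liked the strategy, not whether staff became more or less satisfied with delivering PrEP.

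The difference has consequences. The Background argues that adding PrEP must not overburden staff, and under Aim 3 the Aim 2 results feed a best-practices document. A favourable approval score could be read there as evidence that a strategy improved HCW satisfaction.

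**Working it through.** **Step 1. Who can answer which item.** Section 12.3.6 describes the client satisfaction question as being about services, and the HCW question as being about training and modifications. Set against the design of Section 12.3.1:

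| Clinics and period | Client item (services) | HCW item (training and modifications) |
|---|---|---|
| Intervention, baseline | can be rated | nothing yet to rate |
| Intervention, after introduction | can be rated | can be rated |
| Comparator, first three months | can be rated | nothing to rate |
| Comparator, last three months | can be rated | nothing to rate |

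The client item fills four cells and the HCW item one. With one cell there is neither a change nor a between-group difference. What remains is a mean from at most 20 × 4 = 80 HCW per round. With SD 20 and no clustering its 95% half-width is 1.96 × 20/√80 = 4.4 points.

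**Step 2. The plan's 4 points.** Inputs from Section 12.3.4: two-sided α 0.05, 80% power, SD 20 on a 100-point scale. The section gives neither the formula nor the number per group behind the figure. For two independent means, n per group = 2 × (1.960 + 0.842)² × 20²/4² = 392.4, so 393. The detectable difference is 2.802 × 20 × √(1/n₁ + 1/n₂):

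- 400 against 400 (an inferred size, for example 100 women × 4 clinics): 3.96 points.
- Clients, 960 against 960 (240 × 4): 2.56 points.
- Clients, 480 against 480 before and after (even split assumed): 3.62 points.

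So 4 points lies within reach of client numbers in a simple two-group comparison without clustering.

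**Step 3. HCW numbers, supposing a common item were asked.** Same formula, no clustering:

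- Intervention against comparator, 80 against 80: 56.03 × √(2/80) = 8.9 points; power for 4 points is 24%.
- Before against after, assuming 10 and 10 per clinic, hence 40 against 40: 56.03 × √(2/40) = 12.5 points; power 14%.
- Change against comparators, 40 per cell: 56.03 × √(4/40) = 17.7 points; power 9%.
- All four rounds pooled, 320 against 80 distinct comparator HCW: 7.0 points; power 36%. Counting comparator HCW afresh each round (320 against 320) gives 4.4 points; power 72%.

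**Step 4. Clustering.** The plan gives no intraclass correlation. With assumed values of 0.01 to 0.10, the design effect 1 + 19 × ICC runs from 1.19 to 2.90, and 8.9 becomes 9.7 to 15.1 points. The 12.5 and 17.7 would also grow to the extent that clinic averages shift between periods.

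**Step 5. Scale.** Section 12.3.9 uses 1-10 and Section 12.3.4 uses 100 points. If rescaled linearly over nine units, SD 20 becomes 1.8, and 8.9, 12.5 and 17.7 points become about 0.8, 1.1 and 1.6 units.

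**The case against.** The strongest reply is that HCW satisfaction was always meant as a measure of experience with the intervention. The purpose in Section 12.3.3, the content in Section 12.3.6 and the training-satisfaction source of the scale all point that way, and the planned analysis leaves HCW satisfaction out. This is a fair account of the survey, and it means that no estimator for HCW satisfaction is specified. A reader might infer that a planned HCW analysis will fail; the documents do not go that far. But the reply leaves the impact wording of Aim 2 without data to support it, so one or the other must change.

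A second reply is that the Aim 2 HCW questionnaire is not shown. Section 12.3.8 and the Aim 2 part of Appendix B list only the exit survey and the abstraction tool, and the indicator in Section 12.3.9 is worded generally. A common item could exist. It would therefore be too strong to say that there will be no usable baseline or comparator values; the documents support only that no such item is described. Staff could perhaps rate earlier PrEP training, since all sites already deliver PrEP, but that is a different object from training in the new strategy.

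Third, Aim 2 attaches time to satisfaction, and HCW time is measured by time-and-motion observation. Comparators undergo the same data collection, so that component does have a possible contrast. This stands, but it does not supply a satisfaction score.

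Fourth, the 4 points may concern clients only. The only knowledge outcome is a client one, and Step 2 favours that reading. A reader might take Section 12.3.4 as an HCW power claim; the text does not establish it.

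**Conclusion.** The point holds in limited form. Aim 2 promises an evaluation of impact on HCW satisfaction, while the survey as described can yield only a post-introduction acceptability summary in intervention clinics. This rests on the wording of Sections 12.3, 12.3.1, 12.3.3 and 12.3.6 and needs no calculation. It assumes that the questionnaire contains what Section 12.3.6 describes and nothing more general.

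The figures serve a second purpose. The 12.5 and 17.7 points describe the precision of the repaired design under an assumed even split, independent responses, SD 20 and no clustering; they do not measure the defect. Together with the 8.9 points for 80 against 80, they show that up to 20 HCW per clinic cannot reach 4 points within a round, so that figure should not be read as covering HCW. One of several Aim 2 outcomes is affected; the others are untouched by this point.

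**What to change.** Add one identical HCW item on satisfaction with current PrEP service delivery, parallel to the client question about services. Ask it in both periods in all eight clinics of each round, within the planned 20 HCW per clinic and split between periods, and compare changes between intervention and comparator clinics. Keep the training and modification items as descriptive acceptability, asked in intervention clinics after introduction. Name this comparison in the planned analyses, add the HCW instrument to Section 12.3.8, and use one scale throughout.

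In Section 12.3.4, state that the 4 points applies to client scores. Give the HCW figures separately (about 8.9, 12.5 and 17.7 points before clustering, by contrast) and label the HCW comparison low-precision.

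The cost is one added or reworded item, fewer HCW per period, and a less favourable published figure for HCW. The number of surveys does not change. If the sponsor prefers a purely descriptive outcome, the alternative is to remove HCW satisfaction from the impact list in Aim 2 and report it as acceptability.

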Serial HIV testing for PrEP can be expedited by HIV self-testing in clinics. HIV retesting is required for all clients on PrEP, but the high volume of testing may overburden fixed numbers of HCW, or may shift HCW away from other tasks. Rapid oral HIV self-testing (HIVST), which is saliva-based, has excellent diagnostic performance, with high sensitivity and specificity when compared to standard rapid blood HIV testing [43,44]. HIVST has been used in varied settings and recently been expanded by the Kenya Ministry of Health as an option to increase HIV testing in Kenya. A recent cluster randomized trial in Malawi demonstrated that facility-based HIVST in outpatient waiting areas significantly increased number and proportion of clients tested [45,46]. HIVST for retesting for PrEP users is being tested among serodiscordant couples in Kenya, and is anticipated to increase fidelity (accuracy in adherence) to retesting guidelines, save HCW time, and be more cost-effective.

Policy Implications

Policymakers may consider affordability data, in addition to effectiveness data, to make relevant, local PrEP policy decisions. Cost-effectiveness analyses are useful for comparing interventions against one another; however, interventions considered "cost-effective" by standard Gross Domestic Product thresholds may not be affordable, particularly in resource-limited settings [47,48]. A recent review of PrEP cost-effectiveness called for budget impact analyses to assess affordability [49]. Budget impact analyses quantify total cost when implemented on a large scale, which helps policymakers determine whether a specific intervention is affordable given budget constraints. As Kenya moves towards adopting universal health care this year, this type of analysis will be particularly needed. PrEP is a relatively expensive evidence-based intervention; the Ministry of Health has outlined a series of PrEP cost research questions, including drivers of total cost and cost of delivery through varied service delivery platforms, to direct their roll out of PrEP nationally. Gaps exist in understanding how policymakers use research to make decisions. Systematic reviews have revealed a weak understanding in how policymakers consider scientific evidence in making policy decisions [50]. This study will explicitly address this gap, providing innovative data to promote more rapid translation of research findings into policy.

9) GUIDING FRAMEWORKS

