Proctor Model: A review in 2000 noted that it took, on average, 17 years for just 14% of effective evidence-based interventions to become part of routine clinical practice [51]. While discovery science has tended to dominate HIV research historically, there is a growing recognition of the need for implementation science to bring promising

evidence-based interventions to scale to realize their full impact. Implementation science is a new scientific field; while terminology and definitions are evolving, this application will use NIH terminology and define terminology that is unique to implementation science. The Proctor model characterizes 1) implementation outcomes, 2) service, and 3) client outcomes, noting that implementation strategies are applied to improve implementation of interventions from discovery science [52] (Figure 6). This study will measure: 1) implementation outcomes, including fidelity (proportion of women who receive all PrEP specific steps in a visit: HIV testing, HIV risk screening, PrEP counseling), penetration (proportion of women who are screened for PrEP / total women receiving antenatal or postnatal services), acceptability, uptake, and costs; 2) service outcomes, including efficiency, effectiveness, and timeliness, and 3) client outcomes, including satisfaction. Operational definitions of each outcome are provided in Section 11.3.9 Variables.

Summarizing study results across aims

PRISM framework: We will use the PRISM (Practical, Robust Implementation and Sustainability Model) Model, which synthesizes the RE-AIM framework, Model for Improvement, and the Chronic Care model. This

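### Fidelity is defined as three steps received in one visit, but the Aim 2 procedures count offers under that name

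*Combined protocol and SAP*

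**What the plan says.** Fidelity appears among the Aim 2 outcomes in the executive summary, in section 11 and in section 12.3. The variables table in section 12.3.9 gives the indicator as "Proportion of women who receive all PrEP specific steps in a visit: HIV testing, HIV risk screening, PrEP counseling". Section 9 (Proctor Model) words it the same way. Sections 9, 12.2 and 12.3 all send the reader to the variables table for operational definitions, under the outdated number 11.3.9.

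For sources, the table lists first "Primary data of anonymous exit survey assessing services received", then direct observation of client and provider, then routine registers, including the HIV testing register. It does not rank them. Section 12.3.3 plans "to assess intervention fidelity and client satisfaction through exit surveys with up to 40 clients per month per facility".

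Section 12.3.6, which tells staff what to collect, reads differently. Among the register counts it lists "women offered HIV testing and PrEP (fidelity". The client survey is to collect satisfaction, knowledge and "client perception of being offered PrEP services". Client observation is to characterise efficiency and time.

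**The concern.** Section 12.3.6 puts the label of a defined outcome on a different quantity. A woman can be offered a test and decline it, or be offered PrEP without proper counselling. She would count in the register figure and not in the outcome as defined. An analyst who took the column tagged as fidelity would report offers as if they were services delivered. A bundle that improved completion of steps without changing offers would then show no gain, and one that only raised offers would appear to improve fidelity.

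The survey wording adds to this. The exit survey is the source best suited to the definition, because one woman can report on all three steps of her visit. If it asks only whether she felt she was offered PrEP services, it does not record receipt either. The surveys are anonymous, so receipt that is not asked about during a round cannot be recovered afterwards.

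**Working it through.** The plan states no baseline, detectable effect or power for fidelity, so it has no figure to reproduce. The main check is a comparison of texts.

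**Definition against procedures**

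- *Defined outcome (12.3.9, and section 9):* receipt, in the same visit, of a test, a risk screen and counselling; all three are required.
- *Register count tagged fidelity (12.3.6):* offer of a test and of PrEP. Screening is counted in the same sentence but under penetration. Counselling is not listed.
- *Client survey (12.3.6):* perceived offer. The table in 12.3.9 says services received.
- *Observation (12.3.6):* efficiency and time only. The table lists observation as a fidelity source, but the procedures do not describe it being used for that.
- *Register abstraction as described for the consent waiver (section 18):* simple counts of people completing each step. This says completion where 12.3.6 says offer. Separate step totals would not show how many women had all three steps.

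None of the three sources, as described in 12.3.6, is committed to the defined outcome.

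**Could the gap be sized?** Only by assumption. Section 12.3.4 assumes 68% for penetration of screening and counselling. Suppose, purely for illustration, that 68% are also offered a test and PrEP, that all of these are screened and counselled, and that a share c complete the test. Defined fidelity is then 0.68 × c:

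- c = 0.80: 54.4%, a gap of 13.6 points from the offer count
- c = 0.90: 61.2%, a gap of 6.8 points
- c = 1.00: 68.0%, no gap

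The values of c are not in the documents, and the offer count stays at 68% only because the example holds it there. This shows that the two measures can diverge. It does not estimate by how much.

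**Precision of the survey compared with registers**

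Women per arm and period (4 facilities, 3 months):

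- exit survey: 40 × 3 × 4 = 480 at most
- registers: 100 × 3 × 4 = 1,200 (the conservative volume in 12.3.4) to 200 × 3 × 4 = 2,400 (the upper volume in 12.3.3)

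The 95% half-width for the difference between arms in before/after change, at p = 0.68, with s the facility-by-period SD, is

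1.96 × √[4 × (0.68 × 0.32 / n + s² / 4)]

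- s = 0: 8.3 points (n = 480), 5.3 (n = 1,200), 3.7 (n = 2,400)
- s = 5 points (assumed): 12.9, 11.1 and 10.5 points

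The survey is less precise, but if facilities vary over time by even this much, the loss is about 2 points.

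**The case against.** The best defence is that the protocol already says which definition governs. Three sections point to the variables table, and section 12.3.6 is a list of counts with one-word tags. Section 12.3.3 gives fidelity to exit surveys, and the table names a survey of services received. On that view, one phrase is loose and nobody would be misled. Much of this stands: there is a governing definition and a suitable source. It does not dispose of the point, because data are collected under the procedures, and these describe offers in both the register count and the survey.

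A second defence is that screening is not missing from the registers. That is right: a screening count is collected under penetration.

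A reader might go further and infer that the self-testing bundle is bound to inflate the offer count. Section 8 does say that self-testing "is anticipated to increase fidelity (accuracy in adherence) to retesting guidelines, save HCW time, and be more cost-effective", and section 12.3.2 says "HIVST will be provided as an option in private cubicle-style kiosks". But the section 8 sentence concerns retesting of PrEP users in serodiscordant couples, not the three-step outcome. In section 12.3.2 self-testing is for women already due a repeat test, so an optional method need not add offers. A reader might also infer from Appendix B that the exit survey has no HIV-test item. Appendix B only summarises themes, so this cannot be known.

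Finally, the survey may not detect a modest change. In the illustration, a rise in completion from 80% to 95% moves defined fidelity by 0.68 × 15 = 10.2 points. That exceeds the 8.3-point half-width without clustering but not the 12.9 points with it. This is a fair limit on the remedy. In the same example the offer count would not move at all.

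**Conclusion.** The procedures in section 12.3.6, followed as written, would not produce fidelity as section 12.3.9 defines it. This follows from the text and needs no numerical assumption. The harm is conditional: it arises if the register count, or a survey of perceived offers, is reported under the outcome's name.

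Its size cannot be determined from the documents. The 0 to 13.6 point range above rests on assumed completion rates and includes no gap at all.

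It would be too strong to say that an Aim 2 effectiveness conclusion is compromised. Fidelity is absent from the detectable effects in section 12.3.4 and from the planned time-series comparison in section 12.3.6, so no powered or planned test depends on it. What is at stake is a named outcome that could be mislabelled. It is worth correcting before the rounds begin, because the correction is cheap and receipt cannot be reconstructed later.

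**What to change.** 1. In section 12.3.6, rename the register count *HIV test/PrEP offer* and report it separately from fidelity.
2. Make the exit survey the main source for fidelity, in line with section 12.3.3, with one yes/no receipt item per step: HIV test at this visit by any method, risk screening, and PrEP counselling in person or by video.
3. Change the survey description in section 12.3.6 from perceived offers to services received.
4. Keep registers and observation as checks, and use this one definition in all four rounds.

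The cost is edits to a few sentences and up to three survey items, fewer if the full tool already has them. No register linkage or identifiers are needed, so the consent waiver for abstraction is unaffected. The downside is that the survey is self-reported and smaller, at most 480 women per arm and period, so fidelity will be estimated less precisely than register counts. On the illustrative figures above, a change in test completion alone would have to reach about 12 points without clustering (8.35 / 0.68 = 12.3), or about 19 with a facility-by-period SD of 5 points (12.87 / 0.68 = 18.9), to exceed the survey's half-width.
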